9.4 Pregnancy Reporting

If a female subject or if a female partner of a male subject becomes pregnant during the study, the subject should inform the study site as soon as possible. No additional treatments shall be administered until a serum pregnancy test is performed and confirmed. Upon confirmation of the pregnancy, the female subject will be discontinued from the treatment portion of the study, and requested to continue with the follow-up visits. Any confirmed pregnancy will be tracked and followed through outcome. While pregnancy itself is not considered an AE or an SAE, any pregnancy complications or elective termination of a pregnancy for medical reasons will be recorded as an AE and evaluated as a possible SAE. All pregnancies should be reported to the Sponsor and Ethics Committee.

9.6 Laboratory Tests

All laboratory tests procedures will be referenced in the Central Laboratory Manual.

9.6.1 Pregnancy Test

A urine and serum pregnancy test will be performed at the first Screening Visit (V1) for females of childbearing potential. Samples will be sent to a central laboratory. Pregnancy testing not required for women of non-childbearing potential defined as post-menopausal for at least 2 years or surgically sterile (tubal ligation, oophorectomy, or hysterectomy).

A urine pregnancy test will be performed at the DTH challenge if performed at an additional visit after Screening Visit (V1), at Baseline Visit (V3) and at every other visit during the injection period (Visits 5, 7, 9, 11) and Efficacy Evaluation Visit (V13) at the investigative site for all females of childbearing potential. Urine pregnancy testing not required for women of non-childbearing potential defined as post-menopausal for at least 2 years or surgically sterile (tubal ligation, oophorectomy, or hysterectomy).

Nielsen- CFW-2D Page 42 of 54
Protocol Final version 5.0: 06Dec2016

9.6.2 Clinical Chemistry Analysis
The following clinical chemistry analyses will be performed at the first Screening and Efficacy Evaluation
9.6.3 Clinical Haematology Analysis
A complete blood count
will be performed at the Screening and Efficacy Evaluation Visits (Vis 1 and 13). Samples will be sent to a central laboratory for analysis and reporting.
9.6.4 Urinalysis
Routine urinalysis including blood (
will be performed at the Screening and Effica Evaluation Visits (Visits 1 and 13). Samples will be sent to a central laboratory for analysis and reporting
The following microscopic analysis will be performed when relevant for any positive results:
9.7 Stopping Rules
The following are Stopping Rules that will be applied to individual subjects or treatment cohorts. In addition to the Stopping Rules, the Investigator may discontinue treatment of any subject in which addition treatments are judged to be unsafe or intolerable.
9.7.1 Individual Stopping Rules
9.7.1.1 Immediate Reactions Following DTH or Intralesional Injection
Subjects will remain in the clinic for safety monitoring after DTH or intralesional injection for a minimum 30 minutes after dosing in the event they experience signs and/or symptoms of immediate hypersensitiv and/or anaphylaxis.

Nielsen- CFW-2D
Protocol Final version 5.0: 06Dec2016
Confidential and proprietary. Permission should be obtained before any reproduction.

9.7.1.2 Local Reactions

The following reactions occurring within 7 days following the injection of Investigational Product, as judged by the Investigator based upon the subject diary entries, discussion with subject, and the scale in Protocol Section 9.2.2, also judged by Investigator as possibly, probably, or definitely related to the Study Drug:

[figure not shown]
- Pain (Severity Grade 4)
- Tenderness (Severity Grade 4)
- Erythema/Redness (Severity Grade 4)
- Induration/Swelling (Severity Grades 3-4)

[figure not shown]
If a subject fails to contact the Investigator about the occurrence of a severity Grade 4 local reaction, the Investigator and Medical and Safety Monitor will investigate this event to characterize the severity and grade of the event, before recommending the stopping of the subject.

9.7.1.3 Serious Adverse Events (SAE)

A serious adverse event as defined in Protocol Section 9.3 and is judged as possibly, probably, or definitely related to Study Drug.

Additionally, important medical events that may not result in death, be life-threatening, or require hospitalization may be considered SAEs when, based on appropriate medical judgment, they may jeopardize the subject and may require medical or surgical intervention to prevent one of the outcomes

9.7.2.3 Serious Adverse Events (SAE)

A serious adverse event as defined in Protocol Section 9.3 and is judged as possibly, probably, or definitely related to Study Drug.

Additionally, important medical events that may not result in death, be life threatening, or require hospitalization may be considered SAEs when, based on appropriate medical judgment, they may jeopardize the Subject and may require medical or surgical intervention to prevent one of the outcomes listed in 9.3.

10 DATA QUALITY ASSURANCE/SITE MONITORING

During the study, monitoring visits will be conducted at regular intervals as detailed in the Monitoring Plan. The monitoring visits will be conducted to ensure protocol adherence, quality of data, accuracy of entries on the eCRFs, drug accountability, compliance with regulatory requirements and continued adequacy of the investigational site and its facilities.

The site may be audited and/or monitored by a quality assurance officer named by the Sponsor and/or regulatory authorities may wish to perform on-site audits. The Investigator will be given notice before an audit occurs and will be expected to cooperate with any audit, provide assistance and documentation (including source data) as requested.

11 DATA COLLECTION AND RETENTION

Subject data will be entered in the eCRFs by site personnel. The Data Management Plan (DMP) will define and document the processes and procedures used to ensure consistent, efficient and effective data collection, transfer, storage, quality, and reporting for the study.

The Investigator will maintain source documents for each subject in the study, consisting of case and visit notes (clinical medical records) containing demographic and medical information and the results for any tests or assessments. All information on the eCRFs must be traceable to these source documents in the subject's file. Data not requiring a written or electronic record will be defined before study start and will be recorded directly on the eCRFs, which will be documented as being the source data.

The data collected will be encoded and stored electronically in a database system. AEs will be coded using MedDRA and summarized by SOC, Preferred Term, and treatment group. Summaries by severity and by relationship to study drug will also be included. SAE and discontinuations due to AE will be summarized separately. Concomitant medications will be coded using the World Health Organization Drug Dictionary Nielsen- CFW-2D

Page 45 of 54

Protocol Final version 5.0: 06Dec2016

12 CONFIDENTIALITY OF TRIAL DOCUMENTS AND SUBJECT RECORDS

The Investigator must assure that the subjects' anonymity will be maintained and that their identities are protected from unauthorized parties. On eCRFs or other documents submitted to the Sponsor, subjects should not be identified by their names, but by an identification code. The Investigator should keep a subject enrolment log relating codes with the names of subjects. The Investigator should maintain documents not for submission to Sponsor e.g., subjects' written consent forms, in strict confidence.

13 INVESTIGATOR'S FILES/RETENTION OF DOCUMENTS

The Investigator must maintain adequate and accurate records to enable the conduct of the study to be fully documented and the study data to be subsequently verified. These documents should be classified into two different separate categories: Investigator Study File and Subject Clinical Source Documents.

The Investigator must keep these two categories of documents on file according to country-specific regulation, but no less than US FDA requirements, after completion or discontinuation of the study. After that period of time, the Sponsor will be contacted for long term disposition (Sponsor storage or disposal).

14.2 Analysis Populations

Three populations will be used for the summaries and analyses of the study data. These populations are defined as follows:

Intent-to-Treat (ITT): The ITT Population will consist of all randomized subjects who receive at least one intralesional dose of study medication.

Nielsen- CFW-2D Page 46 of 54

14.3 Subject Disposition

Subject disposition will be summarized by treatment and overall for the Randomized Population.

14.4 Demographic and Baseline Characteristic

Demographic and relevant baseline characteristics will be presented and summarized descriptively by cohort/treatment for the ITT Populations. Additional summary of demographic and baseline characteristics may be specified in the SAP, if deemed necessary.

14.5 Statistical Analysis

General Considerations

Baseline: Baseline refers to the last measurement collected prior to the first dose of randomized study medication at Visit 3 (Day 1).

Placebo: The placebo data from the three cohorts will be assessed for comparability. If the data appear comparable they will be pooled into one placebo group for analyses.

Significance Testing: All statistical testing will be conducted at an α =0.05 significance level. There will be no adjustment of the significance level for multiple comparisons.

14.5.1 Efficacy analysis

14.5.1.1 Analysis of the Primary Efficacy Endpoint

The primary efficacy endpoint is the number and proportion of subjects with the primary injected wart(s) with complete resolution, which will be compared among all treatment groups by using the Cochran-Mantel-Haenszel test with a stratification factor of single versus multiple anatomical regions. Each active treatment will be compared with the pooled placebo in a similar manner.

14.5.2 Safety Analysis

The analysis of safety data will be performed for the ITT Population unless otherwise stated. The primary safety endpoint is the incidence of TEAEs defined as any new AEs or existing AEs that have worsened during or following the first wart(s) injection with CANDIN (Visit 3) through final Follow-up Visit (V15) or Early Termination/Withdrawal. Other safety endpoints include vital signs, physical exams and laboratory measures.

14.5.2.1 Analysis of Adverse Events

TEAEs (those arising after the first intralesional wart injection in this study) will be summarized by treatment, SOC, and preferred term defined by MedDRA. The number of events and number of events by severity, the number of subjects, and the percent of subjects who experienced at least one TEAE will be presented for each SOC and for each preferred term by treatment group. TEAEs that lead to early withdrawals and serious TEAEs will be summarized in the same manner. Additional details will be provided in the SAP. Injection site TEAEs will be analysed separately from other TEAEs.

DTH-related AEs will be analysed separately by Sponsor and Medical Monitor to determine FDA reportability.

14.5.2.2 Analysis of Laboratory Measures

All laboratory results will be listed by treatment, subject, and visit, including scheduled and unscheduled measurements. Laboratory assessments that are outside of normal ranges will be flagged.

Baseline values, the values at each visit, and changes from baseline values will be summarized for each of the quantitative laboratory assessments by treatment.

Shift tables of laboratory results will be used to summarize changes from Baseline to the end of the Follow up Visit (V15) or Early Termination.

14.5.2.3 Analysis of Vital Signs and Physical Examinations

Vital signs at Baseline (Visit 3, Day 1), each scheduled visit, and changes from baseline values will be summarized by treatment. Physical exam findings will be listed.

15 ETHICS

15.1 Local Regulations/Declaration of Helsinki

This study will be conducted in accordance with the ethical principles that have their origin in the Declaration of Helsinki (2013) and that are consistent with "Good Clinical Practice" ICH Tripartite Guideline (July 2002) and the applicable laws and regulations of the country in which the research is conducted, whichever affords the greater protection to the individual.

Nielsen- CFW-2D
Protocol Final version 5.0: 06Dec2016
Confidential and proprietary. Permission should be obtained before any reproduction.

15.2 Ethical Review

This protocol (and any amendment) as well as appropriate consent procedures and related documents (advertisement, subjects' cards, etc.), will be reviewed and approved by the REB/IRB. This Board must operate in accordance with the current Federal regulations. A letter or certification of approval will be sent by the Investigator to the Sponsor prior to initiation of the study, and also whenever subsequent modifications to the protocol are made.

15.3 Informed Consent

It is the responsibility of the Investigator, or a person designated by the Investigator (if acceptable by local regulation), to obtain written informed consent from each individual participating in this study after adequate explanation of the aims, methods, objectives and potential hazards of the study. It must also be explained to the subjects that they are completely free to refuse to enter the study or to withdraw from it at any time for any reason.

If new safety information results in significant changes in the risk/benefice assessment or any new information that may affect willingness to continue to participate, the consent form should if necessary be updated by the Sponsor or Sponsor's representative and be reviewed by the REB/IRB. All subjects (including those already being treated) should be informed of the new information, given a copy of the revised form and asked to give their consent to continue in the study.

18 APPENDIX A Study Flow Chart

		ening sits	Baseline Visit (Day 1)				Injec	tions V	/isits²				Efficacy Evaluation Visit ¹⁰	Follow-up Visits	
Visit	V1 ¹⁴	V21	V3 ¹	V4	V5	V6	V 7	V8	V9	V10	V11	V12	V13 ¹⁴	V14	V15
Window (days)	-30d to -2d	±4h ⁵			± 2d						± 3d	± 3d	± 7d		
PROCEDURES															
Informed Consent	Х														
Inclusion/Exclusion Criteria	Х		Х												
Demographics	Х														
Medical and Surgical History	Х		Х												
Blood Draw for Safety Labs ¹⁴	Х												Х		
Urinalysis	Х												Х		
Pregnancy Test ³	Х		Х		Х		Х		Х		Х		Х		
Vital Signs (Includes weight and height at screening)	Х		Х	Х	Х	Х	Х	х	Х	х	х	Х	Х		
Physical Examination	Х												Х		
Full Body Dermatologic Examination to identify the presence of any wart type			х				X						Х		х
Presence or absence of common warts in designated anatomical areas			х				х						Х		х
Evaluation of presence or absence of common warts other than the measured			х										Х	х	х

		ening sits	Baseline Visit (Day 1)				Efficacy Evaluation Visit ¹⁰	Follow-up Visits							
Visit	V1 ¹⁴	V2 ¹	V3 ¹	V4	V5	V6	V7	V8	V9	V10	V11	V12	V13 ¹⁴	V14	V15
Window (days)	-30d to -2d	±4h ⁵			1			± 2d	•	•			± 3d	± 3d	± 7d
and mapped injectable common warts															
Common warts measurement and mapping (up to 6 injectable common warts including all primary injectable warts)			х	X	x	х	X	x	x	х	x	X	х	х	х
Evaluation of primary injected wart(s) status				Х	Х	Х	Х	Х	Х	Х	Х	Х	Х	Х	Х
Selection of primary injectable wart(s) ⁹			Х												
Selection and Mapping of non-primary common wart(s) for injection ⁸				х	Х	Х	Х	х	х	х	х	Х			
DTH Challenge Injection (30-min observation period)	X ¹³														
DTH Evaluation		Х													
Blood Draw for Biomarkers Evaluation	X ⁶				X ^{6, 12}								X ⁶		
Randomization			Х												
Intralesional Injection (30-min observation period)			Х	Х	Х	Х	Х	х	х	х	х	Х			
Give Subject Diary/Device	X ⁷		Х	Х	Х	Х	Х	Х	Х	Х	Х	Х			
Review/Retrieve Subject Diary		X ⁷		Х	Х	Х	Х	Х	х	Х	Х	Х	Х		
Retain Diary Device													Х		
Medical Photographs ⁴			Х		Х		Х				Х		Х	Х	Х

		ening sits	Baseline Visit (Day 1)				Injec	tions V	isits²				Efficacy Evaluation Visit ¹⁰	Follow-up Visits	
Visit	V1 ¹⁴	V2 ¹	V3 ¹	V4	V5	V6	V7	V8	V9	V10	V11	V12	V13 ¹⁴	V14	V15
Window (days)	-30d to -2d	±4h ⁵						± 2d					± 3d	± 3d	± 7d
Hypopigmentation and Scarring Assessments ¹¹			Х	Х	Х	Х	Х	Х	Х	х	Х	Х	×	Х	Х
Concomitant Medications	Х	Х	Х	Х	Х	Χ	Х	Х	Х	Х	Х	Х	Х	Х	Х
Adverse Events	Х	Х	Х	Х	Х	Х	Х	Х	Х	Х	Х	Х	Х	Х	Х

1 INTRODUCTION

This document provides a detailed description of the statistical methods and procedures to be implemented during the analysis of Nielsen BioSciences Study CFW-2D.

2 STUDY OBJECTIVES

2.1 Primary Objectives

The primary objective of this study is to assess the efficacy of Candin[®] (*Candida albicans*) treatment in subjects with common warts (*Verruca vulgaris*) by evaluating the number and proportion of subjects with the primary injected wart(s) completely resolved.

2.2 Secondary Objectives

Secondary objectives include the following:

1. To assess the safety and tolerability of Candin.

2.3 Exploratory Objectives

3 STUDY OVERVIEW

3.1 Study Design

This is a placebo-controlled, double-blind (subject, Investigator, and site staff with the exception of unblinded dedicated staff to handle study medication), multi-center, Phase IIa study with 3 dose cohorts, randomized to Candin or placebo in a 3:1 ratio. The main study will be up to 20 weeks (10 doses administered every other week) or until a subject has complete resolution of all injected common warts. Subjects who cannot tolerate dosing every 2 weeks (14 ± 2 days) due to a local tolerance issue may be injected at 3-week (21 ± 2 days) intervals for up to 10 doses, increasing the length of the study to 29 weeks. Subjects will be followed for 4 months after final injection(s) for evidence of new or reoccurring warts and for safety evaluation.

Approximately 156 (male or female) subjects aged 18 to 65 inclusive at the date of consent, with 3 to 20 common warts on hands, feet (excluding soles), limbs, and/or trunk will be included in this study. It is assumed that approximately 80% of the subjects will either complete the study or reach complete resolution. Drop-outs will not be replaced. Refer to Section 9 for sample size and power of the study.

Subjects will be included in three cohorts as follows:

Cohort 1: Approximately fifty-two subjects will receive 0.3 mL of either Candin (n=39) or placebo (n=13) intralesionally in the largest (primary) common wart every second week (14 ± 2 days) for a maximum of 10 injections. If the primary common wart exhibits a complete response, the second largest injectable common wart of all anatomical regions will be injected with the randomized study medication at the same dose. If the second largest common wart exhibits a complete response, the third largest wart of all anatomical regions will be injected. If an injected wart recurs after exhibiting a complete response, it will be re-injected instead of the non-primary injected wart that was injected at the previous visit. This injection strategy will be repeated for a maximum of 10 injections per subject, or until all injectable

common warts exhibits a complete response if that occurs before all 10 injections are used.

Cohort 2: Approximately fifty-two subjects will receive 0.5 mL of either Candin (n=39) or placebo (n=13) intralesionally in the largest (primary) common wart every second week $(14 \pm 2 \text{ days})$ for a maximum of 10 injections. The same procedures will be followed in the event of complete response or recurrence as described for Cohort 1.

Cohort 3: If the safety data from Cohort 2 support continuation of the study (defined as medical assessment of the first eight subjects of Cohort 2 completing three injections), approximately 52 subjects planned for Cohort 3 will receive either 0.3 mL/wart Candin (n=39) or placebo (n=13), with a total per visit not to exceed 1.2 mL. Subjects in Cohort 3 must have injectable common warts in at least 2 different anatomic regions. Candin or placebo will be injected under the largest (primary) wart per major anatomical region (left or right; arm, hand, leg, foot excluding sole, or the torso) for a minimum of two and a maximum of four injections per visit, every second week (14 ± 2 days) for a maximum of 10 visits with injections. No more than one wart per anatomical region will be injected on any given visit. If any primary injected wart exhibits a complete response, the next largest injectable common wart will be injected with the randomized study medication at the same dose (maximum of 4 injections per visit), providing the new injectable wart is not within the same anatomical region as other currently injected warts. (If an injected wart recurs after exhibiting a complete response, it will be reinjected instead of the non-primary injected wart that was injected at the previous visit.) This injection strategy will be repeated for a maximum total of 10 injection visits per subject or until all injectable common warts exhibit a complete response, if it occurs before the end of the 10 injection visits.

Two Follow-up visits are included in the study to further assess the efficacy and safety of the study medication. Follow-up information will be obtained for subjects who discontinue their participation in the study. All procedures scheduled for during Follow-up Visit 1 and Follow-up Visit 2 should be completed for early termination subjects, as well as for those subjects who have complete resolution of all common warts prior to their Efficacy Evaluation visit (V13).

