3.2 Study Procedures and Visit Structure

The study visit schedule and procedures are described in Table 1. The study includes a maximum of approximately 29 weeks of treatment with 1-month (4 weeks) and 4-months (16 weeks) Follow-up visits after the Efficacy Evaluation Visit (V13).

Table 1. Study Procedures and Visit Structure

	Screening Visits		Baseline Visit (Day 1)	Injections Visits ²									Efficacy Evaluation Visit ¹⁰	Follow-up Visits	
Visit	V1 ¹⁴ -30d	V2 ¹	V3 ¹	V4	V5	V6	V7	V8	V9	V10	V11	V12	V13 ¹⁴	V14	V15
Window (days)		±4h ⁵		±2d									±3d	±3d	±7d
Procedure	•													•	
Informed Consent	X														
Inclusion/Exclusion Criteria	X		X												
Demographics	X														
Medical and Surgical History	X		X												
Blood Draw for Safety Labs ¹⁴	X												X		
Urinalysis	X												X		
Pregnancy Test ³	X		X		X		X		X		X		X		
Vital Signs (includes weight and height at screening)	X		X	X	X	X	X	X	X	X	X	X	X		
Physical Examination	X												X		
Full Body Dermatologic Examination to identify the															
presence of any wart type			X				X						X		X
Presence or absence of common warts in designated			37				37						37		37
anatomical areas			X				X						X		X
Evaluation of presence or absence of common warts other			37										37	37	37
than the measured and mapped injectable common warts			X										X	X	X
Common warts measurement and mapping (up to 6															
injectable common warts including all primary injectable			X	X	X	X	X	X	X	X	X	X	X	X	X
warts)															
Evaluation of primary injected wart(s) status				X	X	X	X	X	X	X	X	X	X	X	X
Selection of primary injectable wart(s) ⁹		X													
Selection and Mapping of non-primary common wart(s)			X	v	v	X	X	X	Х	v	Х	X			
for injection ⁸			Λ	X	X	Λ	Λ	Λ	Λ	X	Λ	Λ			
DTH Challenge Injection (30-min observation period)	X^{13}														
DTH Evaluation		X													
Blood Draw for Biomarkers Evaluation	X^6				$X^{6,12}$								X^6		
Randomization			X												
Intralesional Injection (30-min observation period)			X	X	X	X	X	X	X	X	X	X			
Give Subject Diary	X^7		X	X	X	X	X	X	X	X	X	X			
Review/Retrieve Subject Diary		X^7		X	X	X	X	X	X	X	X	X	X		
Medical Photographs ⁴			X		X		X				X		X	X	X
Hypopigmentation and Scarring Assessments ¹¹			X	X	X	X	X	X	X	X	X	X	X	X	X
Concomitant Medications	X	X	X	X	X	X	X	X	X	X	X	X	X	X	X
Adverse Events	X	X	X	X	X	X	X	X	X	X	X	X	X	X	X

- 1. Screening Visit 2 and Baseline Visit may be performed on the same day if all screening information and data are available.

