4 STUDY ENDPOINTS

4.1 Primary Efficacy Endpoint

The primary efficacy endpoint is the number and proportion of subjects with the primary injected wart(s) completely resolved at any treatment or Follow-up visit.

[figure not shown]
In Cohort 1 and 2, the largest common wart located on hands, feet (excluding soles), limbs, and/or trunk will be selected as the primary injected wart. In Cohort 3, the largest common wart per anatomical region (left or right; arm, hand, leg, foot (excluding sole) or the torso) will be selected as the primary injected warts for a minimum of 2 and a maximum of 4 warts. In Cohort 3 subjects, injected warts must be in different anatomical regions. Warts in flat, plantar, facial, periungual, or genital or in a region of pre-existing inflammatory condition are excluded from injection.

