6.6 Concomitant Medications

All medications are to be coded using the current versions of WHO Drug Dictionary and Anatomical Therapeutic Chemical (ATC) classification system.

Medications will be classified as:

- Pre-treatment medications: medications taken and stopped prior to the first dose date.
- Concomitant medications: medications taken after receiving the first injection of the randomized study medication. These belong to the following categories:
 - O Prior concomitant medications: medications started prior to the first dose of randomized study medication and continuing past the first dose date.
 - New concomitant medications: medications started during or after the first dose date of the randomized study medication and prior to the first Follow-up visit (Visit 14).
 - New concomitant medications in Follow-up period: medications started during or after the first Follow-up visit (Visit 14) and prior to the second Follow-up visit (Visit 15).

Number and percent of the Safety subjects with each of the above-mentioned medications will be summarized by ATC classification (ATC level 2 and level 4).

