7.2 Efficacy Analyses

7.2.1 Analyses of Primary Endpoint

If the area of a measured wart at baseline becomes 0 at a post-baseline evaluation visit, the wart will be considered as completely resolved. For each of the four treatment groups, the number and percent of subjects achieving complete resolution of the primary injected wart(s) will be calculated and summarized.

[figure not shown]

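### Two small gaps in the responder count: the mITT drops dosed subjects never re-measured, and the visible text lets clearance after non-study wart therapy count as response

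*SAP*

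**What the plan says.** **Population.** SAP 5.4 defines the mITT as Safety-population subjects with a post-baseline measurement of the primary wart(s), and uses it for all efficacy endpoints. SAP 7.1.4 states that missing data are generally not imputed; its visible exceptions are assay values below quantification and adverse-event dates. The ITT in Protocol 14.2, like the Safety population in SAP 5.3, requires only randomisation and one intralesional dose.

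**Endpoint.** SAP 4.1 counts a subject whose primary wart(s) are "completely resolved at any treatment or Follow-up visit". SAP 7.2.1 gives the rule: "If the area of a measured wart at baseline becomes 0 at a post-baseline evaluation visit, the wart will be considered as completely resolved". Neither sets a condition on what cleared the wart.

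**Follow-up after leaving.** SAP 3.1: "Follow-up information will be obtained for subjects who discontinue their participation in the study". It adds: "All procedures scheduled for during Follow-up Visit 1 and Follow-up Visit 2 should be completed for early termination subjects". The purpose given for these visits is "to further assess the efficacy and safety of the study medication". In SAP Table 1 the row "Evaluation of primary injected wart(s) status" is marked at both follow-up visits, V14 and V15.

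**Other therapy.** Protocol 5.3 discontinues a subject from the study as soon as another wart treatment is introduced. SAP 6.6 has a category for "medications started during or after the first Follow-up visit (Visit 14) and prior to the second Follow-up visit", but no visible text ties it to the responder rule.

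**The concern.** Two things can move the reported proportion away from what was randomised and dosed.

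First, a subject who is dosed and never seen again cannot be shown to have cleared. Removing that subject, rather than counting no resolution, raises the rate in that arm. If such losses differ between arms, the comparison moves too.

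Second, the passages above join up. A subject starts other wart therapy, is discontinued, attends V14 or V15, is found clear, and is a responder for the assigned arm. SAP 2.1 gives the objective as the efficacy of Candin treatment, so clearance by another therapy is not obviously what the proportion should contain. V15 falls 16 weeks after V13 (SAP 3.2), so the period in which this can happen is a large part of the counting time: 16/(20+16) = 44% with 2-week dosing, or 16/(29+16) = 36% with 3-week dosing. Counting every visit whatever the later therapy is a legitimate choice, but the visible text does not present it as one.

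**Working it through.** **Inputs.** Planned rates are 24% on placebo and 70% on active (protocol synopsis, Sample Size Determination). There are 39 CANDIN subjects per cohort and 3 × 13 = 39 pooled placebo (Protocol 6.1; SAP 3.3, Table 2). Tests are two-sided at 0.05 (SAP 7.1.1). The share who neither complete nor resolve is up to 10% in the protocol synopsis and about 20% in SAP 3.1. No document gives a rate of switching, of returning after a switch, or of clearing on other therapy.

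**The plan's own power figure.** The synopsis states 94% with about 52 per arm. The two-sided pooled z test for two proportions gives 99.9% at 52 and 99.8% at 47 (52 × 0.9), so 94% does not reproduce. At the design's 39 per arm it gives 99.1%; exact binomial enumeration of the same test gives 99.0%. Nothing below depends on the 94%. All power figures here ignore the planned stratification.

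**1. mITT.** The planned rates correspond to about 27/39 (69.2%) on CANDIN and 9/39 (23.1%) on placebo, a difference of 18/39 = 46.2 points. Remove never re-measured subjects from the denominator:

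| Removed | CANDIN | Placebo | Difference |
|---|---|---|---|
| none | 27/39 = 69.2% | 9/39 = 23.1% | 46.2 |
| 1 CANDIN | 27/38 = 71.1% | 23.1% | 48.0 |
| 1 placebo | 69.2% | 9/38 = 23.7% | 45.5 |
| 1 in each | 71.1% | 23.7% | 47.4 |

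Each removal adds 1.8 points to CANDIN or 0.6 to placebo. SAP Table 1, note 10 plans the V13 procedures at early termination, so this concerns only subjects never seen after V3.

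**2. Clearance after other therapy, equal share of unresolved subjects.** Let q be the share of otherwise unresolved subjects who leave, use other therapy, return and are clear. Then p' = p + (1 − p)q, and the difference becomes 46 × (1 − q). Moderate case (assumed): 20% leave, half of them switch, and 25% to 50% of those return and clear. So q = 0.20 × 0.5 × 0.25 = 0.025 up to 0.20 × 0.5 × 0.5 = 0.05. The 20% is borrowed from SAP 3.1, where it refers to all subjects; applying it to unresolved subjects is a further assumption.

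| q | Placebo | CANDIN | Difference | Power, 39 per arm (normal approx.) |
|---|---|---|---|---|
| 0 | 24.0% | 70.0% | 46.0 | 99.1% |
| 0.025 | 25.9% | 70.7% | 44.8 | 98.8% |
| 0.05 | 27.8% | 71.5% | 43.7 | 98.3% |
| 0.10 | 31.6% | 73.0% | 41.4 | 96.9% |
| 0.20 | 39.2% | 76.0% | 36.8 | 92.4% |

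The difference shrinks because placebo has more unresolved subjects: 39 × 0.76 = 29.6 against 39 × 0.30 = 11.7.

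**3. Other patterns.** One extra responder is 1/39 = 2.6 points. Equal extra numbers in both arms leave 46 points. One or two extra in placebo only give 43.4 or 40.9; in CANDIN only, 48.6 or 51.1. With no true effect (24% in both arms), the exact rejection rate is 5.2%. Adding 2.5 points to CANDIN only (about one subject) makes it 6.0%; adding 5 points (about two) makes it 8.2%.

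**The case against.** The strongest reply is that the rule may exist in text we cannot see. SAP 7.2.1 is plainly incomplete: it does not show the Cochran-Mantel-Haenszel test that Protocol 14.5.1.1 specifies. Material is also missing around SAP 4.1 and 7.1.4, and SAP 8, the Evaluable definition and Protocol 7.6 are not visible. This stands. The second point is therefore conditional, and a reader should not infer that the plan has been shown to lack a rule.

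Next, the visible protocol may not bring switchers back. Visits after discontinuation appear only for a sponsor or site stop (Protocol 5.3) and for pregnancy (Protocol 9.4). SAP 3.1 goes further. This limits the likely size and leaves two passages to reconcile.

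SAP 6.4 would remove important deviators from an Evaluable population. That could support a secondary analysis, but no visible text says other wart therapy is such a deviation, and SAP 5.4 names the mITT for all efficacy endpoints.

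It is also fair to say that counting every visit and counting clearance after other therapy as non-response answer different questions. This stands too: the documents do not make one the only correct rule, which is why reporting both is the better request.

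Finally, a reader might infer that the SAP replaced the protocol's primary efficacy set. That is not shown. Protocol 14.2 announces three populations but only the ITT is visible, and Protocol 14.5.1.1 names none for the primary test.

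**Conclusion.** Both gaps hold on the visible text, at low severity. The mITT point follows directly from SAP 5.4 and the visible part of 7.1.4. Its size is 1.8 points (CANDIN) or 0.6 points (placebo) per subject never re-measured, and the number of such subjects is unknown but should be small.

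The other-therapy point holds unless unseen text says otherwise. Its likely effect is 1 to 2 points off 46, assuming q between 0.025 and 0.05 and equal in both arms. The harm is mainly to what the estimate means.

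A reader might infer a bias towards CANDIN. The documents do not support that: equal switching among unresolved subjects works the other way, and a gain for CANDIN needs more switching and clearance in that arm of a double-blind trial. A 10-point gain in CANDIN alone, for example, needs 3.9 of its 11.7 unresolved subjects (33%) to switch, return and clear, with none on placebo. Nor is the trial's ability to detect its planned effect in doubt: power is about 98% or more in the moderate case and 92% at q = 0.20.

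**What to change.** 1. **SAP 5.4.** Analyse the primary endpoint in all randomised subjects who received an intralesional dose (the Protocol 14.2 ITT definition, which is also the SAP 5.3 Safety definition). Count those with no post-baseline primary-wart measurement as not resolved. Keep the mITT as supportive.

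2. **SAP 4.1 and 7.2.1**, unless already stated in text not visible. Before unblinding, fix how visits count after non-study therapy to a primary wart, or after systemic or immune-stimulating wart therapy. Report the primary endpoint both ways: resolution first recorded after such therapy as non-response, and all visits regardless of other therapy. In Cohort 3, apply the rule to each primary wart.

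3. **SAP 3.1 against Protocol 5.3 and 9.4.** Reconcile what these passages say about follow-up visits after discontinuation.

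The cost is some SAP wording, one more table and slightly lower reported response rates. Medication start dates are already needed for the SAP 6.6 categories. The sponsor should check that wart procedures, the wart treated and the dates are also recorded, since SAP 6.6 covers medications only.
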